The sponsor has created a list of AESIs based on current knowledge of the Ad26.COV2.S vaccine. Background incidence rates for most of the data sources and AESIs are available on the VAC4EU dashboard <https://vac4eu.org/covid-19-tool/>. Definitions and codes are available on Zenodo (<https://zenodo.org/communities/vac4eu/>).

Covariate definition

Feasibility Assessment

In the feasibility assessment, covariates will be assessed at the time of COVID-19 vaccine administration (index date).

Safety Evaluation Study

For the cohort analysis, covariates for the study populations will be defined at the index date. For the SCRI design, time-varying covariates will be identified both at the start of the risk window and the control window.

Covariates will be used to define and describe the study cohorts and populations of special interest and their baseline characteristics and/or to control for confounding. Additional covariates may be added during the conduct of the study if deemed important. The look-back observation period to define covariates of interest will be all available information before the index date in each data source with a minimum of 12 months, except when an alternative look-back window is specified.

Data Sources

The study will use data from secondary electronic health record databases that are population-based. All data sources will have the ability to provide data on COVID-19 vaccines, outcomes (diagnoses, procedures, laboratory results, and treatments), and important covariates. It is not currently known the extent to which COVID-19 vaccines, product types, and batch numbers will be captured in data sources. To be included in the study, data sources should preferably be updated at a minimum once every 3 months. At the proposal stage, members of VAC4EU were offered the option to participate in the study. Four data sources from 3 countries (Spain, the Netherlands and Italy) will be included in the study. A more detailed description will be included in the VAC4EU FAIR Catalogue.

When establishing the agreements with the data sources to conduct the study, it will be emphasized that the current list of AESIs may be expanded during the course of the study to accommodate newly identified AESIs.

Study Size

The study will be conducted in a source population of approximately 18.1 million individuals, although children will not be vaccinated. It is assumed that up to 10% will be vaccinated with the Ad26.COV2.S vaccine.

Main Statistical Methods

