8.3.4. Covariate Definition

Feasibility Assessment

In the feasibility assessment, covariates will be assessed at the time of COVID-19 vaccine administration or time-matched non-vaccinated individuals.

Safety Evaluation Study

Covariate assessment for the description of the patient population at baseline (index date) will use all available time of enrolment in the corresponding data source (minimum required enrolment period is 1 year).

Covariates will be assessed at index date (for the cohort design) to define patient populations of special interest or priority vaccination groups, to define subgroups of interest for sensitivity analyses, or to control for confounding.

We will consider the following time-varying covariates and corresponding period of evaluation for the SCRI measured at start of the risk window and the control window. To capture use of medications of interest during the month prior to start of the study periods (i.e., risk control and control risk), we will consider the drug supply covering the month prior to the start of the two periods of interest.

- Analgesics (month prior)
- Antibiotics (month prior)
- Antiviral medications (month prior)
- Systemic Corticosteroids (month prior)
- Immunosuppressant therapy (month prior)
- Non-steroidal anti-inflammatory drugs (month prior)
- Heparin (month prior)
- Novel oral anticoagulants (month prior)
- Warfarin (month prior)
- Aspirin (month prior)
- Influenza vaccine (month prior)
- Any pneumococcal vaccine (month prior)
- Any herpes zoster vaccine (month prior)

-
- Human papillomavirus vaccine (month prior)
 - Meningitis vaccine (month prior)
 - Pregnancy (at start of each window of interest)
 - COVID-19 infection (month prior)

For the cohort design, covariate status for all time-varying factors will be measured at index date. All covariates will be assessed in specific periods. For the secondary analysis in dedicated subgroups or patients with a past history, any time prior as the look-back period for the assessment of the covariates will be used, reference point is index date. For vaccinations other than COVID-19, follow-up time will be censored in a sensitivity analysis.

Population characteristics will be identified based on diagnoses, medicines, laboratory data, survey observation or medical observations, and observation period information.

Demographic characteristics

- Age
- Sex
- Pregnancy

Pregnancy status and pregnancy trimester at index date.

- Frailty

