The eFI frailty score as described by Clegg et al ([Clegg 2016](#)) with a count of the number of different conditions will be created. Details will be available in the SAP.

Comorbidities (any time prior)

- Cancer (other than non-melanoma skin cancer)
- Chronic kidney disease (exclusion for acute kidney injury)
- Acute coronary syndrome (exclusion for cardiac/cardiovascular events)
- Chronic respiratory disease (chronic obstructive pulmonary disease, asthma)
- Obesity
- Down's syndrome
- Type 1 (excluded for type 1 when AESI) or type 2 diabetes
- Prior thrombosis (exclusion for thrombosis as outcome – see [Table 1](#))
- Morbidity index: number of different ATC codes (Level 5) dispensed in the year prior to cohort entry
- History of anaphylaxis
- History of any type of allergic reaction
- Immunocompromised conditions (will be used to define subgroups for secondary analyses)

-
- Immunodeficiencies
 - Systemic Immunosuppressant medication use
 - Human immunodeficiency virus and other immunosuppressing conditions
 - Parkinson’s disease
 - Stroke/brain injury
 - Dementia
 - Difficulty walking
 - Chronic use of home oxygen (>3 months of continuous use)
 - Palliative care
 - Heart failure (exclusion for heart failure as an outcome).

Covid-19 History

- Prior recorded COVID-19 infection as yes/no for the feasibility studies and by severity for the final study (non-hospitalised, hospitalised)

Comedication (dispensed/prescribed/used in period or episode covering this period)

- Analgesics (month prior)
- Antibiotics (month prior)
- Antiviral medications (month prior)
- Systemic Corticosteroids (month prior)
- Non-steroidal anti-inflammatory drugs (month prior)
- Psychotropics (year prior)
- HMG-CoA Reductase Inhibitors (statins) (year prior)
- Novel oral anticoagulants (month prior/time-varying)
- Warfarin (month prior)
- Aspirin (month prior)
- Oral contraceptives (year prior)
- Hormone replacement therapy (year prior)
- Heparin (month prior)
- Immunosuppressants
- Use of antihypertensive drugs.

Vaccinations

- Administration of any other COVID-19 vaccine from the reference date until the end of the follow-up period (censoring criterion)

-
- Influenza vaccine (month prior/time-varying)
 - Any pneumococcal vaccine (month prior/time-varying)
 - Any zoster vaccine (month prior/time-varying)
 - Human papillomavirus vaccine (month prior/time-varying)
 - Meningitis vaccine (month prior/time-varying).

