Health Care Utilisation in the Year Before and in the 4 Weeks Prior to Index Date

- Number of individuals with at least one hospitalisation (hospitalisation data sources)
- Number of individuals with at least one GP-visit (Primary care data sources)
- Number of different dispensed/prescribed drugs ATC Level 5 dispensed (all data sources)

The AESI may have different sets of risk factors, and outcome-specific analyses may contain different covariate sets. Potential covariates may include the following information, as available in each data source. For the SCRI design, covariate status will be measured at start of risk window and control window for time-varying factors.

For the secondary analyses in subgroups, the following categories will be used:

- Immunocompromised individuals,
- Pregnant women,
- Prior COVID-19 infection,
- Individuals who have a prior history of thrombotic events or thrombocytopenia,
- Individuals with a prior history (ever) of that event (i.e., more than a year before).

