8.4.1. SIDIAP (ES) (7 million Active Individuals)

The Information System for Research in Primary Care (Sistema d'Informació per al Desenvolupament de la Investigació en Atenció Primària' [SIDIAP]; www.sidiap.org) was created in 2010 by the Catalan Health Institute and the IDIAP JGol Institute. It includes information collected since 01 January 2006 during routine visits at 278 primary care centres pertaining to the Catalan Health Institute in Catalonia (North-East Spain) with 3,414 participating GPs. SIDIAP has pseudo-anonymised records for 7 million people (80% of the Catalan population) and is highly representative of the Catalan population. The SIDIAP data comprise the clinical and referral events registered by primary care health professionals (e.g., GPs, paediatricians, and nurses) and administrative staff in electronic medical records, comprehensive demographic information, community pharmacy invoicing data, specialist referrals, and primary care laboratory test results. The SIDIAP data can also be linked to other data sources, such as the hospital discharge database, on a project-by-project basis. Health professionals gather this information using ICD-10-CM codes, ATC codes, and structured forms designed for the collection of variables relevant to primary care clinical management, such as country of origin, sex, age, height, weight, body mass index, tobacco and alcohol use, blood pressure measurements, and blood and urine test results. Regarding vaccinations, SIDIAP includes all routine childhood and adult immunisations, including the antigen and the number of administered doses. Encoding personal and clinic identifiers ensures the confidentiality of the information in the SIDIAP database. Currently, with the COVID-19 pandemic, there is the possibility to have shorter-term updates in order to monitor the evolution of the pandemic. Recent reports have shown the SIDIAP data to be useful for epidemiological research. SIDIAP is listed under the ENCePP resources database.

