The General Practitioner databank comprises data from electronic patient records registered by GPs. The records include information on diagnoses and symptoms, laboratory test results, referrals to specialists, and health care product/drug prescriptions. The prescription records include information on the type of product, prescription date, strength, dosage regimen, quantity, and route of administration. Drug prescriptions are coded according to the WHO ATC coding system. Diagnoses and symptoms are coded according to the International Classification of Primary Care (ICPC) [www.nhg.org], which can be mapped to the International Classification of Diseases (ICD) codes but can also be entered as free text. General practitioner data cover a catchment area representing 3.2 million residents (~20% of the Dutch population).

The Outpatient Pharmacy Databank comprises GP- or specialist-prescribed health care products dispensed by the outpatient pharmacy. The dispensing records include information on the type of product, date, strength, dosage regimen, quantity, route of administration, prescriber speciality, and costs. Drug dispensing is coded according to the WHO ATC classification system. Outpatient pharmacy data cover a catchment area representing 4.2 million residents (~25% of the Dutch population). The PHARMO Database Network is listed under the European Network of Centres for Pharmacoepidemiology and Pharmacovigilance (ENCePP) resources database. PHARMO GP databank captures vaccinations supplied by the GP (influenza, zoster, COVID-19).

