As of 08 May 2021, ~65,000 doses of Ad26.COV2.S vaccine have been administered in the Netherlands. Assuming PHARMO covers ~20% of the Dutch population, this should be 16,250 doses in PHARMO's catchment area. However, different healthcare providers administer the COVID-19 vaccines (i.e., GPs, the public health service and healthcare institutions) in the Netherlands. The vaccination data are recorded in a central register (if people have given permission beforehand), the COVID-19 vaccination Information and Monitoring System. PHARMO is currently exploring the possibilities to link with this register. Until then, the GP Database will be the basis for the vaccination data. The GP Database contains vaccinations administered by GPs and by the public health service, as GPs receive an automated notification when a patient has a positive corona test or has been vaccinated via the public health service (as long as people have given their consent).

It is difficult to estimate how many persons will be vaccinated with Ad26.COV2.S vaccine during the study period in the Netherlands. The Dutch government wants everyone from the age of 18 to have had at least one dose of COVID-19 vaccine by the beginning of July 2021. This vaccination schedule depends on many factors (e.g., approval and effectiveness, delivery and distribution of vaccines to injection sites, such as hospitals and GPs, new developments and advice from, for instance, the Health Council of the Netherlands (i.e., de Gezondheidsraad). Also, the choice of the type of vaccination depends on different factors, such as type of work (care workers), home living (yes or no), year of birth and existing comorbidities. PHARMO acknowledges that the data source they have access to includes data on vaccine delivery and registration and undertakes to cooperate in addressing the Study objectives by contributing to providing reports based on such data.

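### The cohort reads influenza vaccination only in the month before the index date, so at index dates outside the influenza season the covariate is near zero in both arms and cannot show or adjust for a difference in vaccine acceptance

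*Protocol*

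**What the plan says.** Section 8.3.4 gives the cohort covariate as "Influenza vaccine (month prior/time-varying"). The time-varying label has no effect in this design: "For the cohort design, covariate status for all time-varying factors will be measured at index date". The Abstract sets a general look-back of all available history "with a minimum of 12 months, except when an alternative look-back window is specified". The month-prior window is such an exception, so it displaces the 12-month default. Section 8.3.4 names control of confounding among the purposes of the cohort covariates. The same one-month window for influenza vaccine appears in that section's list for the self-controlled risk interval (SCRI) design.

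Primary-care contact is listed as "Number of individuals with at least one GP-visit (Primary care data sources"), under the heading "Health Care Utilisation in the Year Before and in the 4 Weeks Prior to Index Date".

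Section 8.7.2.1 matches on year of birth, sex, pregnancy, immunocompromised state, prior COVID-19, calendar time and presence of a risk factor for severe COVID-19. None of these measures vaccine acceptance. Section 8.7.1.2 describes imbalance by absolute standardised differences and adjusts for, or builds a propensity score from, factors found to be imbalanced.

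On availability, section 8.4.1 says "SIDIAP includes all routine childhood and adult immunisations", and section 8.4.3 says "PHARMO GP databank captures vaccinations supplied by the GP (influenza, zoster, COVID-19").

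**The concern.** A one-month window suits the SCRI, where the question is whether another vaccine was given shortly before a risk or control window. In the cohort the useful question differs: do people who accepted Ad26.COV2.S also accept other vaccines, and so differ in health behaviour and in how readily disease is diagnosed? Influenza vaccination in the last season is a recorded trace of that. Influenza vaccination in the last month is not, unless the index date falls in the influenza vaccination season.

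Section 8.9 states that beliefs influencing vaccine behaviour cannot be considered because they are unrecorded or incompletely recorded. A partial stand-in is recorded in at least two of the sources, but the stated window discards most of it.

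The comparison at stake is Ad26.COV2.S versus unexposed for the non-acute events, where the cohort is the primary design. If vaccinees attend and are tested more, the rate ratio for a condition such as autoimmune thyroiditis rises without a vaccine effect. Healthier behaviour among vaccinees would push it down.

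**Working it through.** The protocol gives no figure on this point. The cohort study-size table (Table 2) is unaffected.

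**Step 1: when index dates fall.** Section 6.1 dates the EU authorisation to 11 March 2021. Section 8.4.3 reports about 65,000 Dutch doses by 8 May 2021 and adds that "The Dutch government wants everyone from the age of 18 to have had at least one dose of COVID-19 vaccine by the beginning of July" of 2021. Section 8.1.2.2 gives the unexposed person an index date in the same calendar week, so both arms share the season. Spring and summer dates are therefore plausible for many people, but no distribution is stated and entry can continue later.

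**Step 2: prevalence of the month-prior flag.** Flag prevalence = seasonal coverage × share of the season's doses given in the month before index. Both inputs are assumptions, as is the autumn timing of influenza vaccination.

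| Assumed coverage | Off-season, share 0-2% | In season, share 30% | Full-season look-back |
|---|---|---|---|
| 15% | 0-0.3% | 4.5% | 15% |
| 30% | 0-0.6% | 9% | 30% |
| 60% | 0-1.2% | 18% | 60% |

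**Step 3: what the balance check would see.** Standardised difference = (p1 − p0) / √{[p1(1 − p1) + p0(1 − p0)]/2}. Assume true coverage of 40% versus 20%.

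- 12-month look-back: 0.20 / √[(0.24 + 0.16)/2] = 0.20/0.447 = 0.45.
- Month prior, 2% of doses: 0.8% versus 0.4%, giving 0.004 / √[(0.00794 + 0.00398)/2] = 0.004/0.0772 = 0.05.
- Month prior, 1% of doses: 0.4% versus 0.2%, giving 0.002 / √[(0.00398 + 0.00200)/2] = 0.002/0.0547 = 0.04.

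**Step 4: crude confounding.** Factor = [1 + p1(RR − 1)] / [1 + p0(RR − 1)], using the three bias parameters named in section 8.9. Prevalences and risk ratios (RR) are assumed.

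| p1 v p0 | RR 1.2 | RR 1.5 |
|---|---|---|
| 40% v 20% | 1.08/1.04 = 1.04 | 1.20/1.10 = 1.09 |
| 50% v 20% | 1.10/1.04 = 1.06 | 1.25/1.10 = 1.14 |

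**Step 5: how much the month-prior flag removes.** Take 40% v 20%, RR 1.5 and 2% of doses in the month. Among people with a negative flag, coverage is (0.40 − 0.008)/0.992 = 39.5% versus (0.20 − 0.004)/0.996 = 19.7%. The factor is 1.1976/1.0984 = 1.090, against 1.091 without the flag. Adjusting for it changes almost nothing.

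**Step 6: the GP-visit flag.** Assume 2 to 8 contacts a year, Poisson or negative binomial with k = 1. The chance of at least one visit is 67-100% over the year and 13-46% over four weeks. The year flag is near constant only under some of these assumptions, and the four-week flag clearly varies.

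**The case against.** The influenza item stands among five non-COVID vaccines that all carry the same window, and Table 5 links such vaccines to a sensitivity analysis that censors on them. It can fairly be read as a recent co-vaccination variable, never offered as a proxy for vaccine acceptance. The protocol also allows covariates to be added and leaves adjustment details to the SAP. That explains the window, but section 8.3.4 also gives control of confounding as a purpose of the cohort covariates, and the protocol fixes a specific window that displaces its own 12-month default. This is a stated choice, not a missing detail.

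A reader might infer that the care-seeking covariates as a group hardly vary. The documents do not support that. Section 8.3.4 also lists the four-week GP flag, hospitalisation in both windows, a count of distinct drugs in all sources, year-prior statins and psychotropics, and a frailty score. These do vary, although drug counts and frailty mainly track morbidity.

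A reader might also infer that the vaccinated-versus-unexposed rate ratios must remain confounded by the amounts in step 4. Those are crude factors, before matching and covariate adjustment, and what remains afterwards cannot be computed from the documents. Section 8.9 concedes residual confounding and provides for quantitative bias analysis, and Table 5 includes negative controls. These help to detect or bound bias, but they do not replace measuring an available confounder properly. The two active-comparator contrasts, where everyone accepted a vaccine, are much less exposed.

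On scale: with the minimum target of 100,000 exposed, an assumed full year of follow-up and 100 events per 100,000 person-years, each arm has about 100 events. The 95% limits then lie a factor of exp(1.96√(2/100)) = 1.32 from the estimate. Bias of 1.04 to 1.14 is modest beside that, though less so in larger cohorts.

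Replacing the GP flag by a count is a lesser matter of functional form. The wording may be only a descriptive tabulation, and contact counts are not described for every source.

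**Conclusion.** The point holds for the influenza window. At off-season index dates the flag is positive in about 0-1.2% of people under the stated assumptions, against 15-60% with a full-season look-back. It can neither reveal nor adjust for a difference in vaccine acceptance. The result is avoidable residual confounding of unknown size, mainly for the non-acute events against unexposed comparators. For acute events the cohort is only a sensitivity analysis.

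The conclusion rests on assumed influenza coverage, autumn timing of influenza vaccination, and a substantial share of index dates outside the season. Index dates falling in the influenza season would make the flag more informative (4.5-18%). This is a minor but worthwhile improvement, not a flaw that invalidates the comparison.

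**What to change.** In section 8.3.4, for the cohort design only:

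1. Define influenza vaccination as receipt in the 12 months before index, intended to capture the last season. Keep the month-prior flag solely to describe recent co-vaccination, and leave the SCRI list unchanged.
2. Make the 12-month variable a candidate in the standardised-difference check and in the propensity score or adjustment set of section 8.7.1.2, in sources that record it. The protocol says so explicitly for SIDIAP and PHARMO; confirm it for the others.
3. Optionally, where primary-care contacts are available, record prior-year GP contacts as a count or in categories alongside the at-least-one flag.

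The cost is a longer look-back for one variable. Section 8.2.4.3 already requires 12 months of data before index, apart from infants enrolled since birth, and no study-size figure changes.

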8.4. Data Sources

The study will use data from secondary electronic health record databases that are population-based. All data sources will have the ability to provide data on COVID-19 vaccines, outcomes (diagnoses, procedures, laboratory results, and treatments), and important covariates. It is not currently known the extent to which COVID-19 vaccines, product types, and batch numbers will be captured in data sources. To be included in the study, data sources should preferably be updated at a minimum once every 3 months. At the proposal stage, members of VAC4EU (<https://vac4eu.org/>) were offered the option to participate in the study. Four data sources from 3 countries (Italy, Spain, and The Netherlands) countries will be included in the study. A more detailed description will be included in the [VAC4EU FAIR Catalogue that Molgenis](https://www.molgenis.org/) based (<https://www.molgenis.org/>).

When establishing the agreements with the data sources to conduct the study, it will be emphasized that the current list of AESIs may be expanded during the course of the study to accommodate newly identified AESIs.

